10. LIST OF FINAL REPORT TABLES, LISTINGS AND FIGURES

The Tables, Figures and Listings (TFL) TOC provides the list of tables/listings and figures needed for the study report. It also identifies the tables eligible for each analysis and their role (synopsis, in-text, post-text, SHS, CTRS,...). Note that all TFL aimed to be included as post-text are noted as post-text even if these are tabulation of individual data such as listing of SAE. The post-text material contains all source material for the study report and accordingly a post-text table may be redundant with an in-text table.

The following group names will be used in the TFLs, to be in line with the T-domains:

Table 3 Groups Labels

Group order in tables	Group label in tables	Group definition for footnote
1	10-10-10-AS	2 doses of AS01E-adjuvanted NTHi/Mcat vaccine containing 10 µg of PD, PE-PilA and UspA2
2	10-10-3-AS	2 doses of AS01E-adjuvanted NTHi/Mcat vaccine containing 10 µg of PD, PE-PilA and 3 µg of UspA2
3	PLACE2	2 doses of saline solution (Step 1 + Step 2)

The following sub-group names will be used in the TFLs

Sub-group order in tables	Sub-group label in tables	Sub-group definition for footnote
1	50-59 years	50-59 years old subjects
2	60-71years	60-71 years old subjects

CONFIDENTIAL204913 (NTHI-MCAT-006 EXT:001)
Statistical Analysis Plan Final

11. ANNEX 1 STANDARD DATA DERIVATION RULE AND STATISTICAL METHODS

11.1. Statistical Method References

Confidence intervals The exact two-sided 95% CIs for a proportion within a group will be computed using the Clopper-Pearson exact CI method [Clopper CJ, Pearson ES. *The use of confidence or fiducial limits illustrated in the case of binomial*. Biometrika. 1934;26:404-413].

The standardised asymptotic two-sided 95% CI for the group difference in proportions is based on the Newcombe asymptotic method [method six from Robert G. Newcombe, *Interval estimation for the difference between independent proportions: comparison of eleven methods*, Statist Med. 1998; 17, 873-890].

Concentration greater or equal to a given assay limit of quantification (e.g. 153 EU/ml for anti-PD antibody) is defined as binary variable for non-missing values as:

=1, if concentration is superior or equal to the given assay limit of quantification

=0, otherwise

GMC will be calculated using the following formula:

$$10^{\left\{ \frac{\sum_{i=1}^n \log_{10}(t_i)}{n} \right\}}$$

where t_1, t_2, \dots, t_n are n observed immunogenicity concentrations.

Log-transformed immunogenicity values are normally distributed.

GMR measures the changes in immunogenicity concentrations *within* subjects. The GMR will be calculated using the following formula:

$$10^{\left\{ \frac{\sum_{i=1}^n \log_{10}(\gamma_{ij} / \gamma_{ik})}{n} \right\}} = 10^{\left\{ \frac{\sum_{i=1}^n \log_{10}(\gamma_{ij}) - \log_{10}(\gamma_{ik})}{n} \right\}}$$

Where, for n subjects, γ_{ij} and γ_{ik} are observed immunogenicity concentrations for subject i at time-points j and k , $j \neq k$.

k: baseline

Duration in the study is defined in days as:

Last visit date (visit x)^a – Enrolment date (visit Month 20) + 1

CONFIDENTIAL

204913 (NTHI-MCAT-006 EXT:001)

Statistical Analysis Plan Final

^a or premature discontinuation date (in case of withdrawal from the study). The duration is missing if one of the dates is missing or incomplete.

11.2. Standard data derivation

11.2.1. Date derivation

- Statistical Analysis System (SAS) date derived from a character date: In case day is missing, 15 is used. In case day & month are missing, 30June is used.
- Onset day for an event (ae, medication, vaccination,...): The onset day is the number of days between the last study vaccination & the onset/start date of the event. This is 0 for an event starting on the same day as a vaccination. See SAS date derived in case the start date of the event is incomplete.
- Duration: Duration of an event is expressed in days. It is the number of days between the start & the stop dates + 1. Therefore, duration is 1 day for an event starting & ending on the same day.
- Association of an event to the primary epoch: An adverse event belongs to the primary epoch, if the onset date is before and excluding Visit 6 or the last contact date, whichever is coming first.

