## 3. STUDY DESIGN OVERVIEW

**Figure 1** Study design overview

BS H = blood sample for humoral immune responses;

Rando = randomisation; LV= Last Visit of NTHi-Mcat-001 study; V = Visit of NTHi-Mcat-006 study ; M = Month; VAC = vaccination (indicated in grey);

\* With a cigarette smoking history  $\geq 10$  pack-years (calculation pack-years = average number of cigarettes smoked per day  $\times$  number of years smoked)/20

Protocol waivers or exemptions are not allowed unless necessary for the management of immediate safety concerns. Therefore, adherence to the study design requirements, including those specified in the outline of study procedures (Section 5.5), are essential and required for study conduct.

- Experimental design: Phase I, controlled, multi-centric, single-country, long term follow-up study with three parallel groups from NTHi-Mcat-001 study.
- Duration of the study: For each subject, the study will last approximately 30 months.
- Epoch 001 : Long-term follow-up starting at Visit 1 (Month 20) and ending at Visit 6 (Month 50).
- Primary completion Date (PCD): last subject of Visit 6 (Month 50).

Refer to [glossary of terms](#) for the definition of PCD.

**CONFIDENTIAL**204913 (NTHI-MCAT-006 EXT:001)  
Protocol Amendment 1 Final

- End of Study (EoS): Last testing results released for samples collected at Visit 6.

Refer to [glossary of terms](#) for the definition of EoS.

- Study groups of NTHi-Mcat-001 study:

- **10-10-10-AS:** Up to 30 subjects who have received two doses of the AS01E-adjuvanted GSK Biologicals' NTHi-Mcat investigational vaccine during STEP 2 of NTHi-Mcat-001 study containing 10µg of PD, PE-PilA and UspA2.
- **10-10-3-AS :** Up to 30 subjects who have received two doses of the AS01E-adjuvanted GSK Biologicals' NTHi-Mcat investigational vaccine during STEP 2 of NTHi-Mcat-001 study containing 10µg of PD, 10µg of PE-PilA, and 3.3µg of UspA2.
- **PLACE2 :** Up to 30 subjects who have received two doses of placebo (saline solution) during STEP 2 of the NTHi-Mcat-001 study.

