## **8.2. Detecting and recording serious adverse events**

### **8.2.1. Time period for detecting and recording serious adverse events**

The time period for collecting and recording SAEs will begin at the first study visit and will end at study conclusion following last study visit for each subject. See Section [8.3](#) for instructions on reporting of SAEs.

All SAEs leading to withdrawal from the study will be collected and recorded from the time of the first study visit.

All SAEs related to the study vaccine(s) that occurred since the end of the primary study NTHi-Mcat-001 (201281) will be collected retrospectively, after informed consent is obtained.

In addition to the above-mentioned reporting requirements and in order to fulfil international reporting obligations, SAEs that are related to study participation (i.e. protocol-mandated procedures, invasive tests, a change from existing therapy) or are related to a concurrent GSK medication/vaccine will be collected and recorded from the time the subject consents to participate in the study until she/he is discharged from the study.

The time period for collecting and recording of pIMDs will begin at the first study visit and will end at study conclusion following the last study visit. See section [8.3.4](#) for instructions on reporting of pIMDs.

An overview of the protocol-required reporting periods for SAEs is given in [Table 8](#).

**CONFIDENTIAL**204913 (NTHI-MCAT-006 EXT:001)  
Protocol Amendment 1 Final**Table 8 Reporting periods for collecting safety information**

Event	Visit 1	Visit 2	Visit 3	Visit 4	Visit 5	Visit 6	Study Conclusion
	Month 20	Month 26	Month 32	Month 38	Month 44	Month 50	Month 50
SAEs							
pIMDs							
Intercurrent medical conditions*							

\* Medical conditions that, by potentially altering the immune response of a subject (except pregnancies), may lead to a subject being eliminated from analysis.

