4.2. Secondary endpoints

- Occurrence of any SAE, during the entire study period in all subjects.
- Occurrence of any pIMD during the entire study period in all subjects.

CONFIDENTIAL204913 (NTHI-MCAT-006 EXT:001)
Statistical Analysis Plan Final

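### SAP 11.2.1's strict upper bound leaves SAEs and pIMDs that start on the day of Visit 6 or last contact outside the only epoch, and date imputation can move earlier onsets out too

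*SAP*

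**What the plan says.** SAP 11.2.1 assigns an adverse event to the primary epoch "if the onset date is before and excluding Visit 6 or the last contact date, whichever is coming first". The rule has a strict upper bound and no lower bound. The same section completes partial dates: "In case day is missing, 15 is used. In case day & month are missing, 30June is used".

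Protocol 8.2.1 sets the collection periods. For SAEs, collection "will end at study conclusion following last study visit for each subject". For pIMDs, "collecting and recording of pIMDs will begin at the first study visit and will end at study conclusion following the last study visit". The SAE endpoint in SAP 4.2 is "Occurrence of any SAE, during the entire study period in all subjects", and the pIMD endpoint has the same span. Protocol section 3 defines one epoch, Epoch 001, which ends at Visit 6.

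SAP section 6 opens by sending the reader to Annex 1 for standard derivation rules. SAP 6.3.1 then calls for the number and percentage of subjects with at least one SAE, with an exact 95% CI, and the same for pIMDs. It attaches no analysis window to either table.

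**The concern.** A strict bound does no harm when a later epoch picks up the boundary day. Here no later epoch exists, so an SAE or pIMD starting that day is collected under the protocol and lies within the endpoint, yet has no epoch. The day is an active one: Visit 6 includes a blood draw and the recording of SAEs and pIMDs (Protocol 5.5).

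The epoch rule is the only annex rule that ties an event to a period, and section 6 relies on the annex. A programmer could reasonably use it to select events for the SAE and pIMD tables. Safety is the only secondary objective, groups hold at most 30 subjects, and Protocol 1.2.1 says that pIMDs are to be watched closely because of the adjuvant. A single omitted event would be visible in the results.

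**Working it through.** The plan states no event count or rate, so there is no figure to reproduce. The check compares the windows, then applies the rules literally.

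**1. Windows side by side**

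| Place | Upper limit |
|---|---|
| SAP 11.2.1, epoch rule | strictly before the earlier of Visit 6 and last contact |
| Protocol 8.2.1, collection of SAEs and pIMDs | study conclusion after the last visit |
| SAP 4.2, endpoints; Protocol 10.7, SAE and pIMD counts | whole study period |
| SAP 6.3.1, participation-related SAEs | study conclusion |
| SAP 6.3.1, deaths and withdrawals due to SAEs | whole study |
| SAP 6.3.1, main SAE and pIMD tables | none given |
| SAP 8.2, final safety analysis | study end |
| SAP 11.1, study duration | last visit date minus enrolment date plus 1, so the last visit day counts |

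Only the epoch rule leaves out the last day.

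**2. Fully dated onset on the boundary day**

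The condition is onset < min(Visit 6, last contact). With onset equal to the bound it is false, so the event is always out. For a subject followed for 30 calendar months, the SAP duration rule gives 913 days (31 August 2017 to 29 February 2020) or 915 days (15 May 2017 to 15 November 2019). The affected share of follow-up is 1/913 to 1/915, or 0.11%.

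**3. Day missing, onset in the month of Visit 6**

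The onset becomes the 15th, and the event is out when 15 ≥ day of Visit 6, that is, on days 1 to 15.

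- Visit dates affected in a 365-day year: 15 × 12 = 180, and 180/365 = 49.3%.
- Same-month pairs with a true onset before Visit 6: seven months of 31 days, four of 30 and one of 28 give 7 × 465 + 4 × 435 + 378 = 5373.
- Pairs pushed out: 12 × (0 + 1 + … + 14) = 12 × 105 = 1260, and 1260/5373 = 23.5%.
- Example: true onset 3 November, Visit 6 on 10 November, imputed onset 15 November: out.
- Opposite case: onset and Visit 6 both on 20 November, imputed onset 15 November: in.

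**4. Day and month missing, onset in the year of Visit 6**

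The onset becomes 30 June, and the event is out when Visit 6 is on or before 30 June: 181/365 = 49.6% of visit dates. Of the pairs with a true onset before Visit 6 in that year, 16290/66430 = 24.5% are pushed out.

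The percentages in steps 3 and 4 assume visit and onset dates spread evenly over the calendar. They apply only to events with partial dates in that month or year, so they are not shares of all events.

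**5. What one event does to a table**

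Clopper-Pearson limits, the method in SAP 11.1, for n = 30:

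- 0/30: upper limit 1 − 0.025^(1/30) = 11.6%, so 0.0 to 11.6%.
- 1/30 = 3.3%: lower limit 1 − 0.975^(1/30) = 0.1%, upper limit 17.2%.

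**6. Would one change be enough?**

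An inclusive bound alone still loses day-missing onsets when Visit 6 is on days 1 to 14: 14 × 12 = 168, and 168/365 = 46.0% of visit dates. A cap alone can set the onset equal to the Visit 6 date, which the strict bound still rejects. Both changes are needed.

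**The case against.** The strongest reply is that the rule only labels events. Nowhere do the documents say that a safety table is filtered on the epoch, and every place that describes safety reporting with a stated window uses a wider one (table above). That stands, so omission is conditional. It does not clear the plan: the SAP gives the two main tables no window, and its statement that SAEs and pIMDs at any time in the study are covered concerns recording.

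A reader might infer that deaths on the last day, or SAEs caused by the last blood draw, are dropped from the analysis. The documents do not support this. SAP 6.3.1 gives deaths the whole study and gives participation-related SAEs, which under Protocol 8.2.1 include those from protocol-mandated procedures, a window to study conclusion. The rule also uses onset, so a death on the last day from an SAE that began earlier stays in. The most that can be said is that, if the main tables used the epoch rule, an SAE that began and proved fatal on the day of last contact would be in the death table but not in the SAE table.

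Nor does one draw in six (17%) measure lost events. It counts procedures, and the resulting SAEs have their own window. Nothing in the documents shows that onsets cluster on the last day.

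Two further replies stand in part. Imputation also keeps some same-day events in, as step 3 shows. Reporting within 24 hours (Protocol 8.3.3 and 8.3.4) makes year-only onsets unlikely. For pIMDs, however, that clock starts at awareness of the diagnosis, so the onset may lie well before the report and be less exactly dated.

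**Conclusion.** The point holds as a conflict in the SAP with a conditional effect on the results. It is certain that an SAE or pIMD starting on the day of Visit 6 or last contact, whichever is earlier, falls outside the only epoch, against the protocol's collection period and the SAP's own endpoint and final-analysis windows. This takes the SAP's primary epoch to be the protocol's Epoch 001. It is also certain that the imputation rules can move a genuine pre-visit onset past the bound.

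Omission from the main SAE and pIMD tables follows only if they are programmed on the epoch rule, which the SAP neither states nor excludes. In that case the safety tables would disagree with one another. The number of events affected is probably small and cannot be derived from the documents. One event would move a group of 30 from 0% to 3.3%, with the upper confidence limit rising from 11.6% to 17.2%. The correction is cheap and should be made before the final safety analysis.

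**What to change.** Make three linked changes to the SAP:

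- In 11.2.1, make the upper bound inclusive: onset on or before study conclusion or last contact.
- In 11.2.1, cap any imputed onset at the date of the visit or contact at which the event was reported, since an event cannot begin after it was reported.
- In 6.3.1, state that the SAE and pIMD tables use this window.

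Do not add a lower bound at Visit 1. SAP 8.2 starts the safety data at the parent study's last visit (Month 14), and SAP 6.3.1 brings certain vaccine-related events reported after consent into the analyses. The start of the window should stay consistent with both.

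The cost is a few sentences in the SAP and a small change to the date-derivation and table programs. Data collection and the immunogenicity analysis are unaffected.

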11.2.2. Demography

- Age: Age at the first dose in parent study, computed as the number of units between the date of birth and date of the first dose in parent study. Note that due to incomplete date, the derived age may be incorrect by 1 month when month is missing from the birthdate. This may lead to apparent inconsistency between the derived age and the eligibility criteria/the age category used for randomization.

11.2.3. Immunogenicity

- For a given subject and given immunogenicity measurement, missing or non-evaluable measurements will not be replaced. Therefore, an analysis will exclude subjects with missing or non-evaluable measurements.
- The GMCs calculations are performed by taking the anti-log of the mean of the log titre transformations. Antibody titres below the assay limit of quantification will be given an arbitrary value of half the assay limit of quantification for the purpose of GMC calculation. The assay limit of quantification value is defined by the laboratory before the analysis and is described in the protocol.
- A seronegative subject is a subject whose antibody concentration is below the assay lower limit of quantification (LLOQ). A seropositive subject is a subject whose antibody concentration is greater than or equal to the assay LLOQ.
- The assay LLOQ value is the value under which there is no quantifiable result available. For an assay with a specific 'cut_off' , numerical immuno result is derived from a character field (rawres):

If rawres is 'NEG' or '-' or '(-)', numeric result= cut_off/2,
 if rawres is 'POS' or '+' or '(+)', numeric result = cut_off,

CONFIDENTIAL

204913 (NTHI-MCAT-006 EXT:001)

Statistical Analysis Plan Final

```

if rawres is '< value' and value<=cut_off, numeric result =cut_off/2,
if rawres is '< value' and value>cut_off, numeric result =value,
if rawres is '> value' and value<cut_off, numeric result =cut_off/2,
if rawres is '> value' and value>=cut_off, numeric result =value,
if rawres is '<= value' or '>= value' and value<cut_off, numeric result =cut_off/2,
if rawres is '<= value' or '>= value' and value>=cut_off, numeric result =value,
if rawres is a value < cut_off, numeric result = cut_off/2,
if rawres is a value >= cut_off, numeric result = rawres,
if rawres is a value >= cut_off, numeric result = rawres,
else numeric result is left blank.

```

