**Signature**  
\_\_\_\_\_  
\_\_\_\_\_  
\_\_\_\_\_**Date**  
\_\_\_\_\_  
\_\_\_\_\_

For internal use only

-----Checksum-----!Ver.!Created On - -  
a52942bb02c0cbdc9274680e4d203654ee8eb36e 4.0 7/6/2018 7:02:05 AM - -  
-----

**CONFIDENTIAL**204913 (NTHI-MCAT-006 EXT:001)  
Protocol Amendment 1 Final**Protocol Amendment 1 Rationale**

Amendment number:	Amendment 1
Rationale/background for changes:	

 
• Table 3 of the protocol (Intervals between study visits) was updated as follow:           
 
- Optimal length of interval and allowed intervals were updated to avoid the risk of accumulating up to five shortest or longest allowed intervals with possible anticipation/delay of subject's last visit +/- 100 days from the optimal length of the study.
 
- Footnote 1 was added to Table 3 to specify that the indication of the month of the visit (i.e. Visit 1 [Month 20]) in the Interval column is an approximate period (label) and not an exact requirement to plan the visit during a specific study month.
 
- Footnote 2 was added to Table 3 to define how to count a calendar month for planning the visits.
 
 
 
• The definition of "calendar month" was added to the Glossary of terms.
 
• The protocol was aligned with the Statistical Analysis Plan Amendment, regarding the model used for the immunogenicity analysis.
 
• Table 5 and the laboratory assays appendix were updated with new cut-off values, since new optimized assays have been developed during the study. As the ANCOVA model used for the statistical analysis will include the group category as fixed effects and the pre-Dose 1 concentration in NTHi-Mcat-001 study as regressor, it is to be noted that pre-Dose 1 antibody concentrations in NTHi-Mcat-001 study were reported using the first generation ELISA with a cut-off of 7 EL.U/mL. However, the 2 assay versions have been shown to be technically aligned, allowing the exploratory comparison of anti-PilA ELISA data between NTHi-Mcat-001 and NTHi-Mcat-006 studies.
 
• The list of contributors was updated.
 
• Minor edits have been made in alignment with the GSK protocol template.
 
	

**CONFIDENTIAL**204913 (NTHI-MCAT-006 EXT:001)  
Protocol Amendment 1 Final**Protocol Amendment 1 Investigator Agreement**

I agree:

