Anti-PilA antibodies will be determined using an ELISA assay developed by GSK Biologicals. Concentration of specific anti-PilA antibodies will be determined, using an in-house made reference serum. The technical cut-off of the assay is 16 EU/mL.

*Anti-UspA2 antibodies*

Anti-UspA2 antibodies will be determined using an ELISA assay developed by GSK Biologicals. Concentration of specific anti-UspA2 antibodies will be determined, using an in-house made reference serum. The technical cut-off of the assay is 38 EU/mL.

**CONFIDENTIAL**204913 (NTHI-MCAT-006 EXT:001)  
Protocol Amendment 1 Final**APPENDIX B CLINICAL LABORATORIES****Table 10 GSK Biologicals' laboratories**

Laboratory	Address
GSK Biological's Clinical Laboratory Sciences, Rixensart	Biospecimen Reception - B7/44 [name]
GSK Biological's Clinical Laboratory Sciences, Wavre-Nord Noir Epine	[name]
GSK Vaccines GmbH Klinische Serologie, Clinical Laboratory Sciences	Gebaeude Z26 [name]

**CONFIDENTIAL**204913 (NTHI-MCAT-006 EXT:001)  
Protocol Amendment 1 Final**APPENDIX C AMENDMENTS AND ADMINISTRATIVE  
CHANGES TO THE PROTOCOL**

GlaxoSmithKline Biologicals SA	
Vaccines R &D	
Protocol Amendment 1	
eTrack study number and Abbreviated Title	204913 (NTHI-MCAT-006 EXT:001)
IND number	16531
EudraCT number	2016-004248-13
Amendment number:	Amendment 1
Amendment date:	Amendment 1 Final: 28 June 2018
Co-ordinating author:	PPD (XPE Pharma & Science for GSK Biologicals)

**CONFIDENTIAL**204913 (NTHI-MCAT-006 EXT:001)  
Protocol Amendment 1 Final**Rationale/background for changes:**

- Table 3 of the protocol (Intervals between study visits) was updated as follow:
  - Optimal length of interval and allowed intervals were updated to avoid the risk of accumulating up to five shortest or longest allowed intervals with possible anticipation/delay of subject's last visit +/- 100 days from the optimal length of the study.
  - Footnote 1 was added to Table 3 to specify that the indication of the month of the visit (i.e. Visit 1 [Month 20]) in the Interval column is an approximate period (label) and not an exact requirement to plan the visit during a specific study month.
  - Footnote 2 was added to Table 3 to define how to count a calendar month for planning the visits.

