- The definition of "calendar month" was added to the Glossary of terms.
- The protocol was aligned with the Statistical Analysis Plan Amendment, regarding the model used for the immunogenicity analysis.
- Table 5 and the laboratory assays appendix were updated with new cut-off values, since new optimized assays have been developed during the study. As the ANCOVA model used for the statistical analysis will include the group category as fixed effects and the pre-Dose 1 concentration in NTHi-Mcat-001 study as regressor, it is to be noted that pre-Dose 1 antibody concentrations in NTHi-Mcat-001 study were reported using the first generation ELISA with a cut-off of 7 EL.U/mL. However, the 2 assay versions have been shown to be technically aligned, allowing the exploratory comparison of anti-PilA ELISA data between NTHi-Mcat-001 and NTHi-Mcat-006 studies.
- The list of contributors was updated.
- Minor edits have been made in alignment with GSK protocol template.

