6.2. Immunogenicity

6.2.1. Analysis of immunogenicity planned in the protocol

The primary analysis will be based on the Per Protocol Set. If, in any study group, the percentage of enrolled subjects with serological results excluded from the Per Protocol Set for analysis of immunogenicity is 10% or more, a second analysis based on the Exposed Set for immunogenicity will be performed to complement the Per Protocol Analysis.

Within group assessment

For each group, at Visit 1 (Month 20), Visit 2 (Month 26), Visit 3 (Month 32), Visit 4 (Month 38), Visit 5 (Month 44) and Visit 6 (Month 50), when blood samples are available for humoral immune response and for each assay:

CONFIDENTIAL

204913 (NTHI-MCAT-006 EXT:001)
Statistical Analysis Plan Final

- Seropositivity rate and their exact 95% CI will be tabulated.
- Adjusted geometric mean concentrations (GMCs) and associated two-sided 95% confidence intervals (CIs) will be computed. These will be obtained from one-way ANCOVA with group as fixed effect and Visit 1 (Day 0) concentration in NTHi-Mcat-001 as regressor.
- Geometric Mean Ratios (GMRs) with respect to Visit 1 (Day 0) in NTHi-Mcat-001 will be calculated for Visit 1 (Month 20), Visit 2 (Month 26), Visit 3 (Month 32), Visit 4 (Month 38), Visit 5 (Month 44) and Visit 6 (Month 50), for each group.
- A graph of the GMCs across the time (Visit 1 (Month 20) to Visit 6 (Month 50)) will be considered. Measures such as the maximum concentration, the time of the peak of concentration will be computed. One graph per strain will be created. Each graph will show the 3 groups.
- For each strain, antibody concentrations distribution will be investigated using Reverse Cumulative Curves.
- Subject graphs of immunogenicity results over time will be provided.

These analyses will also be performed for each level of the following minimisation factor: age (50-59 years vs. 60-71 years).

Between group assessment

Comparative analyses will be exploratory with the aim to characterise the difference between the 10-10-10-AS and 10-10-3-AS groups in humoral immune response.

At each visit, differences in percentages and two-sided 95% CIs between the groups 10-10-10-AS versus 10-10-3-AS, will be calculated and the associated confidence interval for the difference will be constructed using the standardised asymptotic method.

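### Does the change of anti-PilA assay cut-off from 7 to 16 make the planned ratio to Day 0 unreliable enough to need an SAP change?

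*SAP*

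**What the plan says.** The within-group part of SAP 6.2.1 states: "Geometric Mean Ratios (GMRs) with respect to Visit 1 (Day 0) in NTHi-Mcat-001 will be calculated". This is done for each group at all six visits, and again by age stratum. SAP 11.1 adds that "GMR measures the changes in immunogenicity concentrations" within subjects, and defines the GMR as the antilog of the mean log10 ratio of follow-up to baseline.

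For low values, SAP 11.2.3 sets this rule: "Antibody titres below the assay limit of quantification will be given an arbitrary value of half the assay limit of quantification". The limit itself is to be taken from the protocol. The derivation steps that follow are written assay by assay ("For an assay with a specific 'cut_off"), and any numeric result under the cut-off becomes half of it.

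For anti-PilA the protocol gives two cut-offs. Appendix A says of the follow-up assay: "The technical cut-off of the assay is 16 EU/mL". The Amendment 1 rationale, given at the front of the protocol and again in Appendix C, says that "pre-Dose 1 antibody concentrations in NTHi-Mcat-001 study were reported using the first generation ELISA with a cut-off of 7 EL.U/mL". That sentence names no antigen. The next one does: "the 2 assay versions have been shown to be technically aligned, allowing the exploratory comparison of anti-PilA ELISA data between NTHi-Mcat-001 and NTHi-Mcat-006 studies".

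The last version in the SAP's document history is dated 24 October 2017. The protocol amendment that brought in the cut-off of 16 is dated 28 June 2018. Neither document says which floor applies to anti-PilA Day 0 values.

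**The concern.** A ratio of two floored quantities is neutral under no change only if both have the same floor. Here a Day 0 value below 7 could become 3.5, while the same serum level at follow-up becomes 8. A subject whose antibody never moved would then appear to have more than doubled. A subject at 15 on both dates would appear to have lost almost half.

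The placebo group makes the problem visible. It did not receive the antigens, so a reader expects its GMR to be near 1, and a low-baseline placebo group could show a rise with no biological cause. Antibody persistence is the primary objective, and the GMR is the SAP's only within-subject measure of anti-PilA response relative to the level before vaccination. Because the Day 0 floor is not named, two programmers could each follow the SAP and report different ratios from the same data.

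**Working it through.** The documents give no GMR, power or sample-size figure to reproduce, so the check applies the SAP's rule directly.

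**Inputs from the documents.** Day 0 cut-off 7, half = 3.5 (Protocol Amendment 1 rationale). Follow-up cut-off 16, half = 8 (Protocol Table 5 and Appendix A). Floor rule f(c, k) = k/2 if c < k, otherwise c (SAP 11.2.3).

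**One unchanged subject at concentration c.** With version-specific floors the ratio is f(c, 16)/f(c, 7):

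- c below 7: 8/3.5 = 2.29
- c from 7 to under 16: 8/c, from 8/7 = 1.14 down to just above 8/16 = 0.50 (exactly 1.00 at c = 8)
- c of 16 or more: c/c = 1.00

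No single subject can show a value between 1.14 and 2.29, although a group average can. With a common limit of 16 the ratio is f(c, 16)/f(c, 16) = 1.00 everywhere.

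**An unchanged group, simple mixture.** If a share p is below 7 and the rest are at 16 or more, the GMR with version-specific floors is 2.286^p: 1.23 at 25%, 1.51 at 50% and 1.86 at 75%. The shares are assumed.

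**A lognormal group.** Let log10 concentration have mean μ and SD σ. With z = (log10 k − μ)/σ, the mean after flooring at cut-off k is

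m(μ, σ, k) = Φ(z)·log10(k/2) + (1 − Φ(z))·μ + σ·φ(z).

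The GMR is 10 raised to the follow-up mean minus the Day 0 mean. I assume σ = 0.3.

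*Day 0 GMC 5.* The floored Day 0 GMC is 5.00 with cut-off 7 and 8.37 with cut-off 16. After a true two-fold rise the floored follow-up GMC is 10.52.
- Unchanged: 8.37/5.00 = 1.67 version-specific; 8.37/8.37 = 1.00 common.
- Two-fold rise: 10.52/5.00 = 2.10 version-specific; 10.52/8.37 = 1.26 common.

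*Day 0 GMC 8.* The floored Day 0 GMC is 7.39 or 9.45, and the follow-up GMC after a two-fold rise is 14.90.
- Unchanged: 9.45/7.39 = 1.28 version-specific; 1.00 common.
- Two-fold rise: 14.90/7.39 = 2.02 version-specific; 14.90/9.45 = 1.58 common.

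The same formula for other cases at σ = 0.3:

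| Day 0 GMC | True rise | Version-specific | Common limit of 16 |
|---|---|---|---|
| 12 | none | 1.05 | 1.00 |
| 16 | none | 0.97 | 1.00 |
| 25 | none | 0.94 | 1.00 |
| 12 | 2-fold | 1.98 | 1.89 |
| 5 | 5-fold | 4.66 | 2.78 |
| 8 | 5-fold | 5.23 | 4.09 |
| 25 | 5-fold | 5.07 | 5.37 |
| 5 | 10-fold | 9.80 | 5.86 |
| 8 | 10-fold | 10.78 | 8.43 |

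At this SD, for true rises of two- to ten-fold and Day 0 GMC from 5 to 25, version-specific floors stay within about 8% of the truth. The common limit falls short by up to 44% (2.78 against 5). With no change, version-specific floors give 0.87 to 1.84 over GMC 5 to 25 and SD 0.2 to 0.4, and 0.98 to 1.00 at GMC 50 or more.

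**The ANCOVA regressor.** The Day 0 floor also enters the adjusted GMC ratios through the covariate. The check used 4000 simulated trials with 30 subjects per group, SD 0.3, correlation 0.6 between Day 0 and follow-up, and a true ratio of 2.5, all assumed. The median adjusted ratio with a Day 0 floor of 3.5 against 8 was 1.95 against 1.94 at Day 0 GMC 8, and 2.40 against 2.38 at GMC 12. The Day 0 floor hardly matters there. Same-visit comparisons use 16 in every group, so the mismatch does not enter their outcome.

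**The case for a change.** The strongest case for a change is that the omission is real and cheap to close. One sentence would name the Day 0 floor, and a small table could give the Day 0 shares below 7, from 7 to under 16, and at 16 or above. The protocol's statement that the assay versions are aligned concerns the measurement scale and does not say how substituted values are treated. The choice is also not trivial: from an assumed Day 0 GMC of 5, a true two-fold rise reads 2.10 or 1.26 depending on the floor. If placebo baselines are low, the floors that the wording favours would show a rise that did not happen.

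All of that stands as description. It does not show that the plan is wrong. The limit is attached to the assay, and the protocol treats the Day 0 ELISA as a separate version with its own cut-off. An analyst would therefore keep parent-study values as reported and use 3.5 and 8. Raising quantified Day 0 results between 7 and 16 to the later limit would need an instruction that neither document contains. That analyst would not be making a poor choice either, because where antibody has persisted from a low baseline, this reading is generally the closer one. The common limit is better when nothing has changed, at the price of understating real rises. The table of Day 0 shares would help a reader but would alter no result.

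**Conclusion.** The SAP omits a detail, and its wording lets an analyst fill it sensibly. Neither floor is uniformly better. Version-specific floors can show a false change in an unchanged group with low baselines (1.67 and 1.28 at assumed Day 0 GMC 5 and 8, SD 0.3). A common limit removes that but understates true rises from the same baselines (1.26 and 1.58 for a true two-fold rise). Replacing one with the other is a trade-off and corrects no error.

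The reach is narrow. One antigen and one summary are affected. Protocol 10.6.1 does not list the within-group GMR, SAP section 7 calls all analyses descriptive, and the Amendment 1 rationale already discloses the two assay versions, "allowing the exploratory comparison of anti-PilA ELISA data between NTHi-Mcat-001 and NTHi-Mcat-006 studies". The stopping rule uses vaccine-to-placebo ratios at the same visit and is touched only through the regressor, where the simulated difference was 0.02 or less.

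The group figures rest on assumed lognormal distributions, because the documents give no Day 0 anti-PilA data. If most Day 0 values were well above 16, the question would disappear. No change to the plan follows. Whoever reads the placebo row of the anti-PilA GMR table should bear the two cut-offs in mind.
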